10.3 Subject Information and Informed Consent

At screening, the investigator will obtain a freely given written consent from each subject after an appropriate explanation of the aims, methods, anticipated benefits, potential hazards and any other aspect of the study which is relevant to the subject's decision to participate. The informed consent form must be signed, with name and date and time noted by the subject and the investigator, before the subject is exposed to any study-related procedure, including screening tests for eligibility.

For subjects not qualified to give legal consent, written consent must be obtained from the legal parent/guardian. If children are old enough to understand the risks and benefits of the study, they should also be informed and provide their written consent.

If the period between screening and treatment is more than 3 months, informed consent will be reviewed and confirmed prior to treatment, and details of the review process will be recorded in the patient chart and indicated by the investigator.

The investigator will explain that the subjects are completely free to refuse to enter the study or to withdraw from it at any time, without any consequences for their further care and without the need to justify. The investigator will complete the informed consent section of the CRF for each subject enrolled.

Each subject will be informed that his/her medical (source) records may be reviewed by the study monitor, a quality assurance auditor or a health authority inspector, in accordance with applicable regulations, and that these persons are bound by confidentiality obligations.

10.4 Protocol Amendments

Any prospective change to the protocol will be agreed between the investigator (co-ordinating investigator in multi-centre studies) and the Sponsor prior to its implementation. Any such amendments will be submitted to the IEC(s/IRB) and/or competent authority responsible as required by applicable regulations. IEC(s)/IRB approval will at a minimum be requested for any change to this protocol which could affect the safety of the subjects, the objective/design of the study, any increase in dosage or duration of exposure to the IMP an increase in the number of subjects treated, the addition of a new test or procedure, or the dropping of a test intended to monitor safety.

10.5 Confidentiality of Subjects Data

The investigator will ensure that the subject's confidentiality is preserved. On CRFs or any other documents submitted to the Sponsor, the subjects will not be identified by their names, but by a unique subject number. Documents not for submission to the Sponsor, i.e., the confidential subject identification code list, original consent forms and source records will be maintained by the investigator in strict confidence.

11 QUALITY CONTROL AND QUALITY ASSURANCE

11.1 Periodic Monitoring

The monitor will contact and visit the investigator periodically to review all study-related source data/records, verify the adherence to the protocol and the completeness, correctness and accuracy of all CRF entries compared to source data. The investigator will co-operate with the monitor to ensure that any discrepancies identified are resolved.

For this study, the first monitoring visit shall take place shortly after the start of treatment of the first subject. Thereafter, monitoring frequency will depend on study progress.

The monitor must be given direct access to source documents (original documents, data and records). Direct access includes permission to examine, analyse, verify and reproduce any records and reports that are important to the evaluation of the clinical study. Source data will be available for all data in the CRFs, including all laboratory results.

11.2 Audit and Inspection

The investigator will make all study-related source data and records available to a qualified quality assurance auditor mandated by the Sponsor, or to IEC/IRB/regulatory inspectors, after reasonable notice. The main purposes of an audit or inspection are to confirm that the rights and welfare of the subjects have been adequately protected, and that all data relevant for the assessment of safety and effectiveness of the IMP have been reported to the Sponsor.

12 REPORTING AND PUBLICATION

12.1 Clinical Study Report

A clinical study report (in accordance with relevant guidelines and Sponsor's SOPs) will be prepared by the Sponsor after the completion of the study. The co-ordinating investigator will approve the final study report after review.

12.2 Publication Policy

The results of this study may be published or presented at scientific meetings. If this is envisaged by an investigator, the investigator agrees to inform the Sponsor and to submit all manuscripts or abstracts to the Sponsor prior to submission to an editorial board or scientific review committee. This will allow the Sponsor to protect proprietary information and to provide comments based on information that may not yet be available to the investigator.

In accordance with standard editorial and ethical practice, the Sponsor will support publication of multi-centre studies only in their entirety and not as individual centre data. Authorship will be determined by mutual agreement.

13 LIABILITIES AND INSURANCE

In order to cover any potential damage or injury occurring to a subject in association with the IMP or the participation in the study, Octapharma AG will contract insurance in accordance with local regulations.

The investigator is responsible for dispensing the IMP according to this protocol, and for its secure storage and safe handling throughout the study.

15 APPENDICES

None.

1 INTRODUCTION

This Statistical Analysis Plan (SAP) provides a comprehensive and detailed description of statistical methods to be used to analyze the data for protocol FORMA-02, Version 6.0, 31-Oct-2014, as amended on 08-July-2016 (Version 7.0).

The purpose of this SAP is to outline the planned analyses to be completed to support the completion of the Clinical Study Report (CSR) for protocol FORMA-02. In addition, this SAP will describe any clarifications or modifications to the endpoints and statistical methods in the protocol. The planned analyses identified in this SAP will supersede the statistical sections in protocol and will be included in regulatory submissions and/or future manuscripts. In addition, exploratory analyses not necessarily identified in this SAP may be performed to support the clinical development program. Additional exploratory analyses may be added as addendums to this SAP after the signoff. Any post-hoc, or unplanned, analyses not identified in this SAP performed will be clearly identified in the respective CSR.

2 DESCRIPTION OF THE PROTOCOL

2.1 Protocol Number and Version

FORMA-02, Version 7.0

2.2 Protocol Title

Prospective, open-label, uncontrolled, phase III study to assess the efficacy and safety of Octafibrin for on-demand treatment of acute bleeding and to prevent bleeding during and after surgery in subjects with congenital fibrinogen deficiency.

2.3 Protocol Date

The date of protocol Version 7.0 is 08-July-2016.

FORMA-02	JSS Medical Research - Data Management		
Statistical Analysis Plan			
Form Number: MNI-DM-BIS-01 v 6.0-T1	Current Version Number: 2.0	Previous Version Number: 1.1 9-April-2015	Date:11-July-2016

3 STUDY OBJECTIVES AND ENDPOINTS

3.1 Study Objectives

3.1.1 Primary Objective

The primary objective of the study is:

- To demonstrate the efficacy of Octafibrin for on-demand treatment of acute bleeding episode (spontaneous or after trauma).

3.1.2 Secondary Objectives

- To show an association between the overall clinical assessment of haemostatic efficacy and the surrogate endpoint 'clot strength' or 'clot firmness' (referred to as 'Maximum Clot Firmness' [MCF]) that was used as a surrogate endpoint for haemostatic efficacy and determined via Thromboelastography (TEG) in the pivotal Pharmacokinetic (PK) study FORMA-01. Therefore, MCF as surrogate efficacy parameter will be determined before first infusion and 1 hour after the end of first and last infusion.
- To achieve peak target plasma fibrinogen level of 100 mg/dL in minor bleeds and 150 mg/dL for major bleeds 1 hour post-infusion.
- To determine the response to Octafibrin based on incremental in vivo recovery (IVR).
- To demonstrate the efficacy of Octafibrin in preventing bleeding during and after surgery.
- To assess the safety of Octafibrin in subjects with congenital fibrinogen deficiency, including immunogenicity, thromboembolic complications, and early signs of allergic or hypersensitivity reactions.

FORMA-02	JSS Medical Research - Data Management	 JSS <small>RESPONSIVE RELIABLE RESULTS</small>	
Statistical Analysis Plan			
Form Number: MNI-DM-BIS-01 v 6.0-T1	Current Version Number: 2.0	Previous Version Number: 1.1 9-April-2015	Date:11-July-2016

3.2 Study Endpoints

3.2.1 Primary Endpoint

The primary endpoint is:

- The primary endpoint is the overall clinical assessment of haemostatic efficacy of Octafibrin in treating the first documented bleeding episode of each patient. The first bleeding episode covers the time period from the first Octafibrin infusion until 24 hours (i.e., 1 day) after the last infusion or the end of the treatment observation period, whichever comes last.

The investigator's overall clinical assessment of haemostatic efficacy for bleeding will be based on a 4-point haemostatic efficacy scale (see table below). The final efficacy assessment of each patient will be adjudicated by the Independent Data Monitoring & Endpoint Adjudication Committee (IDMEAC). The number of subjects per outcome category will be assessed in the final analysis.

Category	Definition
Excellent	Immediate and complete cessation of bleeding in the absence of other haemostatic intervention as clinically assessed by the treating physician; and/or <10% drop in haemoglobin compared to pre-infusion.
Good	Eventual complete cessation of bleeding in the absence of other haemostatic intervention as clinically assessed by the treating physician; and/or <20% drop in haemoglobin compared to pre-infusion.
Moderate	Incomplete cessation of bleeding and additional haemostatic intervention required, as clinically assessed by the treating physician; and/or between 20 and 25% drop in haemoglobin compared to pre- infusion.
None	No cessation of bleeding and alternative haemostatic intervention required, as clinically assessed by the treating physician; and/or >25% drop in haemoglobin compared to pre-infusion.

FORMA-02	JSS Medical Research - Data Management		
Statistical Analysis Plan			
Form Number: MNI-DM-BIS-01 v 6.0-T1	Current Version Number: 2.0	Previous Version Number: 1.1 9-April-2015	Date:11-July-2016

3.2.2 Secondary Endpoints

The secondary efficacy endpoints are:

- MCF assessment before first infusion and 1 hour after end of first and last infusion of each documented bleeding episode.
- Fibrinogen plasma level before and 1 hour after the end of each infusion as well as at the time of the overall clinical assessment of haemostatic efficacy (i.e., 24 hours after the last infusion of each documented bleeding episode).
- Response as indicated by incremental IVR, calculated as the maximum increase in plasma fibrinogen (Clauss data) between pre-infusion and 1 and 3 hours post-infusion.
- Efficacy of Octafibrin in all bleeding episodes collected in the study using the investigator's overall clinical assessment of haemostatic efficacy for bleeding based on a 4-point haemostatic efficacy scale.

Efficacy of Octafibrin in surgical prophylaxis will be assessed at the end of surgery by the surgeon and post-operatively by the hematologist using the following scales:

Category	Definition
Intra-operative efficacy as assessed by surgeon (at the end of the surgery = after last suture)	
Excellent	Intra-operative blood loss* was lower than or equal to the average expected blood loss for the type of procedure performed in a subject with normal haemostasis and of the same sex, age, and stature.
Good	Intra-operative blood loss* was higher than average expected blood loss but lower or equal to the maximal expected blood loss for the type of procedure in a subject with normal haemostasis.
Moderate	Intra-operative blood loss* was higher than maximal expected blood loss for the type of procedure performed in a subject with normal haemostasis, but haemostasis was controlled.
None	Haemostasis was uncontrolled necessitating a change in clotting factor replacement regimen.

*All excludes unexpected blood loss due to surgical complications, i.e.,

- Direct injury of a vessel (artery or vein)
- Vessel injury not adequately responding to routine surgical procedures achieving haemostasis
- Accidental injury of parenchymatous tissue (e.g., liver, lung)

FORMA-02	JSS Medical Research - Data Management	 RESPONSIVE RELIABLE RESULTS
Statistical Analysis Plan		
Form Number: MNI-DM-BIS-01 v 6.0-T1	Current Version Number: 2.0	Previous Version Number: 1.1 9-April-2015
Date:11-July-2016		

Post-operative efficacy as assessed by haematologist

Excellent	No post-operative bleeding or oozing that was not due to complications of surgery. All post-operative bleeding (due to complications of surgery) was controlled with Octafibrin as anticipated for the type of procedure.
Good	No post-operative bleeding or oozing that was not due to complications of surgery. Control of post-operative bleeding due to complications of surgery required increased dosing with Octafibrin or additional infusions, not originally anticipated for the type of procedure.
Moderate	Some post-operative bleeding and oozing that was not due to complications of surgery; control of post-operative bleeding required increased dosing with Octafibrin or additional infusions, not originally anticipated for the type of procedure.
None	Extensive uncontrolled post-operative bleeding and oozing. Control of post-operative bleeding required use of an alternate fibrinogen concentrate.

An overall efficacy assessment taking both the intra- and post-operative assessment into account will be adjudicated by the IDMEAC. In the event that any intra- or post-operative endpoint data differ between the investigator's assessment and the adjudicated assessment by the IDMEAC, the endpoint will be that based on the adjudicated assessments based on an agreed algorithm as indicated in the IDMEAC charter.

The surgical observation period starts with the first dose of Octafibrin administered prior to elective surgery (Day 1) and, depending on the severity of the event, will last at least 3 post-operative days for minor and 7 post-operative days for major surgeries or until the day of the last post-operative infusion, whichever comes last.

In addition, the location, severity and type of surgery will be documented. Expected and actual duration of surgical procedure and details of administered dose(s) of Octafibrin (pre-, intra- and/or post-operatively) will be recorded. Fibrinogen plasma levels (pre-, intra-, and post-operatively) will be measured. Details of concomitantly administered products (except standard anaesthesia) along with a brief narrative describing the outcome of the intervention will be recorded.

The safety endpoints are:

- Vital signs.
- Physical examination.
- Check of Wells criteria for deep venous thrombosis (DVT) and PE (pulmonary embolism).
- Routine clinical laboratory assessment, including coagulation parameters.
- Adverse events (AEs), including thromboembolic complications and early signs of allergic or hypersensitivity reactions.
- Immunogenicity testing at Day 14 and Day 30 after the administration of Octafibrin for bleeding.

FORMA-02	JSS Medical Research - Data Management		
Statistical Analysis Plan			
Form Number: MNI-DM-BIS-01 v 6.0-T1	Current Version Number: 2.0	Previous Version Number: 1.1 9-April-2015	Date:11-July-2016

4 STUDY METHODS

4.1 Study Design

This is a multinational, multi-centre, prospective, open-label, uncontrolled, Phase III study to assess the efficacy and safety of Octafibrin for on-demand treatment of acute bleeding and to prevent bleeding during and after surgery in subjects with congenital fibrinogen deficiency

A minimum of 24 subjects will be enrolled in the study to assess on-demand treatment of at least one bleeding episode. This will include at least 4 subjects aged between 12 and 18 years (only 18 and above in Russia). This will also include an assessment of at least 4 surgical procedures, 2 of which should be performed in subjects aged between 12 and 18 years (only 18 and above in Russia). The study will be conducted in approximately 15 centres worldwide.

During the study observation period, enrolled patients will be treated for any bleeding episodes or planned surgeries that can be managed under the protocol. Patients may remain in the study until the 24th patient has at least one documented bleeding episode. The study will be considered completed when a minimum of 24 subjects have at least one documented bleeding episode. The study as a whole should be completed within 5 years.

4.2 Study Rationale

It is estimated that there are 500 to 1000 subjects with congenital fibrinogen deficiency in the European Union (EU). Historically, the principal source for the treatment of congenital fibrinogen deficiency has been cryoprecipitate. Plasma-derived and viral-inactivated fibrinogen concentrates are proven to be safer and more specific in the treatment of congenital fibrinogen deficiency compared to cryoprecipitate.

The introduction of Octafibrin will present an additional and safe option, providing more choices of supply for the benefit of the medical community and subjects affected by congenital fibrinogen deficiency.

This phase III study is designed as a multinational, multi-centre, prospective, open-label, uncontrolled study to assess the efficacy and safety of Octafibrin for on-demand treatment of acute bleeding in subjects with congenital fibrinogen deficiency.

As there are currently no guidelines concerning fibrinogen concentrates in either the United States (US) or the EU, this pivotal study was designed following the European Medicines Agency (EMA) "Guideline on the Clinical Investigation of Recombinant and Human Plasma-Derived Factor IX Products" (CHMP/BPWP/144552/2009) and discussions with the Paul Ehrlich Institute and the Paediatric Committee (PDCO) of the EMA.

FORMA-02	JSS Medical Research - Data Management		
Statistical Analysis Plan			
Form Number: MNI-DM-BIS-01 v 6.0-T1	Current Version Number: 2.0	Previous Version Number: 1.1 9-April-2015	Date:11-July-2016

4.3 Study Duration

4.3.1 Planned Duration for an Individual Subject

For subjects receiving on-demand treatment.

- the individual **subject observation and follow-up period** for each documented episode starts with the first dose of Octafibrin administered for on-demand treatment of an acute bleeding episode (Day 1) and will be followed for up to Day 30.
- Each subject's **treatment observation period** is defined according to the severity of the event and will last at least 3 days for minor and 7 days for major bleeding episodes.

For subjects undergoing surgical prophylaxis.

- the **surgical observation period** starts with the first dose of Octafibrin administered prior to elective surgery (Day 1) and, depending on the severity of the event, will last at least 3 post-operative days for minor and 7 post-operative days for major surgeries or until the day of the last post-operative infusion, whichever comes last.

During the study observation period, enrolled patients will be treated for any bleeding episodes or planned surgeries that can be managed under the protocol. Patients may remain in the study until the 24th patient has at least one documented bleeding episode.

As many bleeding episodes or surgeries as possible occurring throughout the study observation period will be documented. Only the first bleeding episodes will be used for the analysis of the primary endpoint (see Section 3.2.1). All bleeding episodes documented in the study will be assessed as a secondary endpoint (see Section 3.2.2).

Patients who were screened for the study but do not present with a bleeding episode or planned surgery during the study observation period will be considered 'no treatment' patients.

The individual observation period by subject starts with the first dose of Octafibrin administered for on-demand treatment of an acute bleeding episode or prior to elective surgery (Day 1). Subjects enrolled will be treated for any bleeding episodes or planned surgeries during the study observation period. They may remain in the study until the 24th subject has at least one documented bleeding episode.

4.3.2 Planned Duration for the Study as a Whole

The study will be considered completed when a minimum of 24 subjects have at least one documented bleeding episode. The study as a whole should be completed within 5 years.

The estimated start of the study (enrolment of first subject) is in the 4th quarter of 2014, and the estimated end of the study (last visit of last subject) is in the 4th quarter of 2019.

FORMA-02	JSS Medical Research - Data Management		
Statistical Analysis Plan			
Form Number: MNI-DM-BIS-01 v 6.0-T1	Current Version Number: 2.0	Previous Version Number: 1.1 9-April-2015	Date:11-July-2016

4.4 Study Population

4.4.1 Safety Population

The safety population will include all subjects who received at least one infusion of the IMP. The analysis of safety will be based on the safety population.

4.4.2 Full Analysis Set (FAS)

The full analysis set defined according to the intention-to-treat (ITT) principle will include subjects who fulfill all of the following conditions:

- Received at least one infusion of the IMP.
- Entered the study with a confirmed congenital fibrinogen deficiency (second inclusion criterion).
- Presented with an episode of acute bleeding (third inclusion criterion).
- And/or plan to undergo a surgical procedure with a need for at least one infusion of the IMP (third inclusion criterion).

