3.2.2 Surgical Prophylaxis

Subjects planning to undergo elective surgery may also be enrolled in the study.

Within 3 hours prior to surgery, each patient will receive a loading infusion of *Octafibrin* to achieve a recommended fibrinogen plasma level of 100 mg/dL for minor surgeries and 150 mg/dL for major surgeries.

Each subject's **surgical observation period** starts with the first dose of *Octafibrin* administered prior to elective surgery (Day 1) and, depending on the severity of the event, will last at least 3 post-operative days for minor and 7 post-operative days for major surgeries or until the day of the last post-operative infusion, whichever comes last.

On each post-operative day, fibrinogen plasma levels will be measured daily (i.e., at least 3 post-operative days for minor and 7 post-operative days for major surgeries) to determine whether additional infusions of *Octafibrin* are needed.

- Additional infusions of Octafibrin should be administered if the actual fibrinogen plasma level measured on subsequent days is below the accepted lower limit of the target level (80 mg/dL for minor surgeries, 130 mg/dL for major surgery).
- If the fibrinogen plasma level is greater than or equal to the accepted lower limit of the target fibrinogen plasma level, *Octafibrin* **should not** be administered.

The actual treatment duration will be determined by the investigator based on his/her judgement of the subject's condition.

All AEs, including thromboembolic events and early signs of allergic or hypersensitivity reactions, occurring between first infusion of IMP before the start of surgery and the Last Post-Operative Day will be recorded.

All SAEs occurring after the first IMP infusion will be documented and reported for a patient throughout the duration of the patient's participation in the study or as required to meet local regulations. Also, any concomitant medications used to treat an SAE will be recorded.

At the end of the study (i.e., when the 24th patient has had at least one treated bleeding episode), all patients will be asked to return for a Study Completion Visit.

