4.4.3 The Per Protocol (PP) Population

The per-protocol (PP) population will include all subjects of the full analysis set who fulfill all of the following conditions:

- Provide valid, i.e., non-missing haemostatic efficacy data.
- Provide a 1-hour post-infusion MCF value.
- Received $\geq 90\%$ of the planned total dose of the IMP in the first infusion.
- Received $\geq 80\%$ of the calculated dose (no dose was calculated, 0% will be assumed) of the IMP over all further infusions according to the treatment schedule
- Did not meet any of the following exclusion criteria:
 - Bleeding disorder other than congenital fibrinogen deficiency.
 - End-stage liver disease (i.e., Child-Pugh-score B or C).
 - Suspicion of an anti-fibrinogen inhibitor as indicated by previous IVR, if available < 0.5 (mg/dL)/(mg/kg).
 - Treatment with any fibrinogen concentrate or other fibrinogen-containing blood product within 2 weeks prior to start of treatment for the bleeding episode or surgery.
- Did not use any coagulation-active drug (i.e., non-steroidal anti-inflammatory drugs, warfarin, coumarin derivatives, platelet aggregation inhibitors) within 1 week prior to start of treatment for the bleeding episode or surgery, or as a planned or expected medication during the time period from Day 1 until 24 hours (i.e., 1 day) after the last Octafibrin infusion.
- Surgical procedure with a need for at least one infusion of the IMP with an overall clinical assessment of haemostatic efficacy.

FORMA-02	JSS Medical Research - Data Management		
Statistical Analysis Plan			
Form Number: MNI-DM-BIS-01 v 6.0-T1	Current Version Number: 2.0	Previous Version Number: 1.1 9-April-2015	Date:11-July-2016

Any protocol deviations other than those with respect to the above conditions for the PP population must be agreed upon in writing by the Sponsor and the study statistician, and in any case, before database closure.

The efficacy analysis will be performed for bleeding events using the full analysis set (ITT analysis) and for the PP population (PP analysis). An additional analysis will also be performed for the surgical population.

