6 GENERAL CONSIDERATIONS FOR STATISTICAL ANALYSIS

The descriptive statistics for continuous variables will be presented with number (n) of non-missing observations, mean, Standard Deviation (SD), median, minimum and maximum (or range). For categorical variables, descriptive statistics will be presented with number of eligible subjects and number (n) with percentage of observations in the various categories of the endpoint, where percentage will be based on the eligible subjects in the respective analysis set.

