6.3 Handling of Drop-outs and Missing Values

In general, if not stated differently, missing data will not be imputed.

If the haemostatic efficacy assessment is missing it will be set to "none" in the ITT analysis. Subjects with missing haemostatic efficacy assessment will be excluded from the per-protocol PP population. LOCF (Last observation carried forward) approach will be used for body weight measurement for all analysis involving dose/kg BW.

Missing MCF and IVR values will not be replaced.

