8 EFFICACY ANALYSIS

8.1 Primary Efficacy Analysis

For bleeding efficacy, the primary endpoint is the overall clinical assessment of the haemostatic efficacy of Octafibrin in treating the first documented bleeding episode of each patient.

The first bleeding episode covers the time period from the first Octafibrin infusion until 24 hours (i.e., 1 day) after the last infusion or the end of the treatment observation period, whichever comes last. Frequency distribution will be provided for the haemostatic efficacy scale data. In addition, a 95% CI for the success rate in haemostatic efficacy (excellent or good) according to Casella (Blyth-Still-Casella interval) will be computed using StatXact® software.

For the following subjects the haemostatic efficacy outcome will be set to the worst category i.e., "none":

- Subjects who withdraw from the study due to lack of efficacy.
- Subjects receiving cryoprecipitate, or concentrates containing fibrinogen other than the IMP between first infusion and efficacy assessment (unless it is clearly documented that these products were administered for reasons unrelated to efficacy [e.g., pharmacy error]).
- Subjects with missing haemostatic efficacy assessment.

Haemostatic efficacy will be displayed by co variables (sex, age groups, race, weight and type of bleeding) in tables or with co variables in listings depending on the number per subgroup.

FORMA-02	JSS Medical Research - Data Management		
Statistical Analysis Plan			
Form Number: MNI-DM-BIS-01 v 6.0-T1	Current Version Number: 2.0	Previous Version Number: 1.1 9-April-2015	Date: 11-July-2016

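### The full analysis set definition contradicts itself and the primary denominator is not limited to treated bleeds, so the rule scoring missing ratings as none could reach surgery-only subjects

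*SAP*

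**What the plan says.** - **Two routes into the trial.** Inclusion criterion 3 accepts either an expected acute bleed or planned elective surgery. Protocol 3.2.2 confirms the second route: "Subjects planning to undergo elective surgery may also be enrolled in the study". SAP 4.1 sets a minimum for surgery: "This will also include an assessment of at least 4 surgical procedures". It does not say how many of these should be in subjects who also have a treated bleed.
- **Full analysis set.** The stem in SAP 4.4.2 says the set "will include subjects who fulfill all of the following conditions". The third condition is an acute bleed. The fourth begins with and/or: "And/or plan to undergo a surgical procedure with a need for at least one infusion of the IMP (third inclusion criterion". Protocol 9.3.2 has the same structure.
- **Set used for the bleeding analysis.** SAP 4.4.3: "The efficacy analysis will be performed for bleeding events using the full analysis set (ITT analysis", with the per-protocol set alongside and an additional analysis for the surgical population.
- **Percentages.** SAP 6: "percentage will be based on the eligible subjects in the respective analysis set".
- **Missing ratings.** SAP 6.3: "If the haemostatic efficacy assessment is missing it will be set to 'none' in the ITT analysis". SAP 8.1 lists, among those given the worst category, "Subjects with missing haemostatic efficacy assessment". SAP 6.2 and the closing paragraph of 8.2 count a missing rating as no success.
- **Surgical set.** SAP 4.4.4 repeats the list from 4.4.2 but joins surgery with a plain and, so it requires both a bleed and surgery.
- **Decision rule.** SAP 8.2 compares the lower limit of the two-sided 95% Blyth-Still-Casella interval with 0.6. It gives a 99.4% probability of at least 20 successes in 24 at a true rate of 0.95.

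**The concern.** A subject who has surgery under Octafibrin and never has a treated bleed has no rating of a first bleeding episode. If that subject is in the full analysis set, and every missing rating in that set becomes none, the subject enters the primary success rate as a failure. The rate would then fall because of how subjects entered the trial, not because of how well bleeds were controlled. The denominator would also exceed the 24 on which SAP Table 1 rests.

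At stake is the only hypothesis test in the plan. Two readings of the same text give two denominators. In an open-label study, that choice should not be left until outcomes are known.

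**Working it through.** **1. Does the text admit surgery-only subjects?** In SAP 4.4.2 the stem requires every condition, which would include a bleed. The last condition is joined by and/or, and the word or has no function if a bleed is always required. SAP 4.4.4 uses the same list with a plain and, so the two definitions are evidently meant to differ. The text of 4.4.2 is contradictory, and its and/or admits a subject treated only for surgery.

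**2. Does anything remove them later?** SAP 4.4.3 names the full analysis set without subsetting it. SAP 6.2, 6.3, 8.1 and 8.2 apply the missing-rating rule without requiring a treated bleed. No sentence limits the primary denominator.

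**3. Reproduce the plan's figures.** Inputs from SAP 8.2: N = 24, true rate 0.95, threshold 0.6, two-sided 95% Blyth-Still-Casella interval. The probability of at least r successes is the sum over x = r to 24 of C(24, x) × 0.95^x × 0.05^(24−x).

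| Successes in 24 | Probability, SAP | Probability, recomputed | Lower limit, SAP | Lower limit, recomputed |
|---|---|---|---|---|
| ≥19 | 0.999 | 0.999 | 0.594 | 0.594 |
| ≥20 | 0.994 | 0.994 | 0.633 | 0.634 |
| ≥21 | 0.970 | 0.970 | 0.691 | 0.692 |
| ≥22 | 0.884 | 0.884 | 0.744 | 0.745 |

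The probabilities agree, and the limits agree to within 0.001. The smallest count that clears 0.6 is 20.

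**4. Apply the literal reading.** Assumption: 24 subjects with a treated bleed, plus s surgery-only subjects all scored none. The denominator is 24 + s, and successes can come only from the 24. For each s, find the smallest count r whose lower limit for r/(24 + s) exceeds 0.6, then take P(X ≥ r) for X ~ Binomial(24, 0.95). The expected observed rate is 24 × 0.95 / (24 + s) = 22.8 / (24 + s). The documents do not give s, so a range is shown.

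| s | N | Successes needed (lower limit) | One fewer (lower limit) | Probability at 0.95 | Expected rate |
|---|---|---|---|---|---|
| 0 | 24 | 20 (0.634) | 19 (0.594) | 0.994 | 0.950 |
| 1 | 25 | 20 (0.613) | 19 (0.569) | 0.994 | 0.912 |
| 2 | 26 | 21 (0.626) | 20 (0.580) | 0.970 | 0.877 |
| 3 | 27 | 22 (0.636) | 21 (0.585) | 0.884 | 0.844 |
| 4 | 28 | 23 (0.643) | 22 (0.594) | 0.661 | 0.814 |

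The decision rule is unaffected at s = 1 and costs little at s = 2. The loss is substantial from s = 3.

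**5. Direction of the error.** Certain failures can only raise the number of successes needed among the 24. At a true rate of 0.6, the chance of passing is 0.013 when 20 are needed (s = 0 or 1), 0.0035 when 21 are needed (s = 2) and 0.0007 when 22 are needed (s = 3). The type I error does not increase.

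**The case against.** A reader might infer that the plan has settled on counting surgery-only subjects as treatment failures. The documents do not support that. SAP 3.2.1 and 8.1 define the endpoint as the outcome of the first documented bleed, over a window that starts with the first infusion for that episode. Without a bleed the endpoint is not applicable, rather than missing. SAP 4.4.3 describes the analysis as one of bleeding events and gives surgery its own analysis. SAP 6 refers to eligible subjects, which leaves room to leave out those who could not have the endpoint. Completion in SAP 4.3.2 is counted in subjects with a bleed, and Table 1 uses N = 24. The bleeding rating is scheduled only in the bleeding flow chart, while surgical subjects have their own ratings. Together these make a bleed-only denominator the probable intent.

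A reader might also take the minimum of 4 surgeries as 4 surgery-only subjects. That does not follow either. The minimum counts procedures, which can be done in subjects who also bleed. A subject enrolled for surgery may stay until the 24th subject has a documented bleed, in a study planned for up to 5 years, and so may later have a treated bleed. Hence s may be 0.

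What remains is that intent has to be inferred. The figure of 24 is a minimum number of subjects with a bleed, not a cap on the full analysis set, and no sentence overrides the literal chain.

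**Conclusion.** The point holds as a defect of definition. SAP 4.4.2 contradicts itself, the primary denominator is not stated, and the missing-rating rule, read literally, can reach subjects who never had a bleed.

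The size depends on s, which the documents do not give, and on the assumption of exactly 24 bleeders with a true rate of 0.95. There is no effect on the probability of success at s = 0 or 1. It falls from 0.994 to 0.970 at s = 2, to 0.884 at s = 3 and to 0.661 at s = 4, where the expected rate drops from 0.95 to 0.814. The error is conservative: it could make an effective product miss the threshold, but it could not produce a false efficacy claim. This should be fixed, but it does not undermine the design.

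**What to change.** Before database lock:

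1. In SAP 4.4.2 and 8.1, define the primary analysis set as subjects with confirmed congenital fibrinogen deficiency and at least one Octafibrin infusion given for an acute bleeding episode. State that this set is the denominator of the primary success rate.
2. In SAP 6.2, 6.3, 8.1 and 8.2, limit the scoring of a missing rating as none to first bleeds that were treated with Octafibrin but not rated.
3. In SAP 4.4.4, remove the acute-bleeding condition, so that surgery-only subjects are analysed in the surgical and safety sets. Without this step, the first change would leave them in no efficacy set.

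With exactly 24 treated bleeders, this restores the SAP's own basis: at least 20 successes needed, with probability 0.994 at a true rate of 0.95. The cost is SAP wording only, with no new data and no change at the sites.
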